4.2.7.4 Analysis of ECG

ECG variables will be summarised with descriptive statistics at each visit and change from baseline summarised for each post-baseline visit by treatment group and for total MEDI3506. Investigators' ECG assessments at baseline versus last observation on treatment will be summarised in shift table by treatment group and for total MEDI3506. Key subject information will be produced for ECG parameter values outside predefined criteria (Table).

In addition, the number and percentage of participants with QTcF intervals (derived as described in Section 3.5.4) at any observation on treatment >450 ms, >480 ms, >500 ms and QTcF increase from baseline >30 ms, >60 ms, >90 ms, and combination of both, will be presented by treatment group and for total MEDI3506.

Individual ECG results and abnormalities in ECG will be listed.

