
To assess the safety and tolerability of MEDI3506 compared with placebo, in adult participants with uncontrolled moderate-to-severe asthma.
	
During the intervention and follow-up periods:
 
 • AEs, SAEs, AESIs • Vital signs • Clinical chemistry, haematology, and urinalysis • ECGs • LVEF as measured by echocardiogram • NT-proBNP • Number of participants seropositive for SARS-CoV-2 at end of study who were seronegative at randomisation visit • For participants testing positive for SARS-CoV-2 (by PCR or serology test), during the intervention and follow-up periods, the number and proportion of patients with COVID-19 AEs/SAEs and the proportion asymptomatic.
Exploratory	

To further assess the longitudinal effect of MEDI3506 compared with placebo on lung function in adult participants with uncontrolled moderate-to-severe asthma.
	
As measured at home, change from baseline up to Week 24 in 2-weekly mean PEF and FEV₁

To assess the effect of MEDI3506 compared with placebo on airway hyperresponsiveness in adult participants with uncontrolled moderate-to-severe asthma.
	
Change from baseline to Weeks 8 and 16 in FEV₁% reversibility.

To assess the effect of MEDI3506 compared with placebo on asthma related inflammatory blood biomarkers in adult participants with uncontrolled moderate-to-severe asthma.
	
Change from baseline to Weeks 1, 4, 8, 12, 16, 20 and 24 in inflammatory blood biomarker levels, including but not limited to:
 
 • CCI • Serum IL-5. • Serum IL-13. • Serum TSLP. 
Change from baseline to Weeks 4, 16, and 24 in plasma EDN.
 
Change from baseline to Weeks 16 and 24 in total IgE.
 
Change from baseline to Week 16 in:
 
 • sST2. • Proinflammatory gene signatures in whole blood.

Table 4 Objectives and Endpoints

Objective	Endpoint
To assess the longitudinal effect of MEDI3506 compared with placebo on small airway function in adult participants with uncontrolled moderate-to-severe asthma.	Change from baseline to Weeks 1, 4, 8, 12, and 16 in airway reactance and resistance as assessed by AO parameters, including but not limited to: 
 • R5 • R20 • R5-R20 • AX

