9.4.4 Safety

The occurrence of AEs and SAE will be described by System Organ Class, Preferred Term, severity, and relationship to the study intervention. Participants will be counted only once for each preferred term, once for each system organ class, and by the highest severity of an event. Number of participants with elevated liver function tests that meet the HL definition will be evaluated. Laboratory evaluations will be summarised with descriptive statistics at each visit and change from baseline summarised for each post-baseline visit. Laboratory measurements will also be summarised based on the number and percentage of participants above or below a pre-specified threshold for each test. The number of participants with clinically significant abnormal ECG results based on investigators' judgments will be summarised at each visit. Change from baseline in vital signs will be summarised by visit.

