3.5.4 Electrocardiogram (ECG)

ECG variables will be collected at visits SV1, SV4, SV10, SV12, and E/D as follows:

- Heart (pulse) rate
- RR interval
- QRS interval

- PR interval
- QT interval

Additionally, QT correction using Bazett's and Fridericia's formulas will be calculated as follows (unless already derived directly from the CRF):

$$QTcB = QT/(RR^{1/2}),$$

$$QTcF = QT/(RR^{1/3}),$$

where QT is measured in msec and RR is measured in sec.

Categorical ECG interpretation (normal, abnormal clinically significant, abnormal not clinically significant) will be provided by the investigator.

Table 19 ECG reference ranges

Parameter	Standard Unit	Lower limit	Upper limit	Change criteria
Heart (pulse) rate	beats/min	<50	>100	
RR interval	ms	<600	>1200	
QRS interval	ms	<80	>120	
PR interval	ms	<120	>200	
QT interval	ms	N/A	>450 male >470 female	+30
QTcB interval	ms	N/A	>450 male >470 female	+30
QTcF interval	ms	N/A	>450 male >470 female	+30

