14.3.8.2 ECG		
Table 14.3.8.2.1	ECG variables, over time	As-treated population
Table 14.3.8.2.2	ECG, baseline versus last observation on treatment	As-treated population
Table 14.3.8.2.3	ECG values outside predefined criteria - key subject information	As-treated population
Table 14.3.8.2.4	QTcF intervals, at any observation on treatment	As-treated population
14.3.8.x Other safety variables		
Table 14.3.8.3	Left ventricular ejection fraction (%), over time	As-treated population

Table 14.3.8.4	NT-proBNP data over time	As-treated population
Table 14.3.8.5	NT-proBNP, baseline to maximum value during treatment	As-treated population
Table 14.3.8.6.1	Number of subjects tested positive for SARS-CoV-2 (by PCR or serology test) at end of study who were tested negative at baseline visit	As-treated population
Table 14.3.8.6.2	Summary of Treatment-emergent Adverse Events of Special Interest by COVID-19 result	As-treated population

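### The protocol promises a by-visit count of investigator-judged clinically significant abnormal ECGs; the SAP tabulates that category only at baseline and the last on-treatment ECG, so Week 24 is left out and the change is not declared.

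*SAP*

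**What the plan says.** - **Protocol 9.4.4 (Safety).** The planned ECG summary is "The number of participants with clinically significant abnormal ECG results", based on investigators' "judgments will be summarised at each visit".
- **Protocol Section 3, Table 4.** ECGs are among the safety endpoints, which are to be assessed "During the intervention and follow-up periods".
- **SAP 3.5.4.** The category needed for the count is collected: "Categorical ECG interpretation (normal, abnormal clinically significant, abnormal not clinically significant) will be provided by the investigator". On timing, "ECG variables will be collected at visits SV1, SV4, SV10, SV12, and E/D".
- **SAP 4.2.7.4.** Investigators' "ECG assessments at baseline versus last observation on treatment will be summarised in shift table" by treatment group and for total MEDI3506. The matching entry in the Appendix C output list is Table 14.3.8.2.2, "ECG, baseline versus last observation on treatment". The other three ECG tables there are variables over time, key subject information for values outside the predefined criteria, and QTcF intervals. None gives the investigator's category by visit.
- **SAP 3.1.4.** The on-treatment phase runs from Day 1 to the last dose date plus 28 days inclusive; anything later is follow-up. SAP Table 8 maps all post-dose ECGs up to Day 141 to Week 16 and those from Day 142 to Week 24. Where several fall in one window, the one closest to the scheduled day is used.
- **SAP Section 6.** The listed changes from Amendment 4.0 contain no ECG entry.

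**The concern.** The protocol names a specific descriptive safety output and the SAP replaces it with a different one without saying so. The replacement is narrower in two ways: it stops at the end of the on-treatment phase, although the safety endpoint runs through follow-up, and it keeps one post-baseline reading per participant.

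The investigator's judgement is the only ECG variable here that captures rhythm, conduction or ischaemic findings as read by a clinician. Intervals and QTcF thresholds do not carry that judgement. Cardiac events, including arrhythmia and myocardial infarction, are an adverse event of special interest (protocol 8.3.7, SAP 3.5.1.1), so a reader of the study report would expect the promised count by arm over the whole safety period.

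The use of the last value also differs from the SAP's practice elsewhere. Laboratory shift tables use the maximum and minimum during treatment (4.2.7.3), NT-proBNP uses the maximum (4.2.7.6), and QTcF categories use any on-treatment observation (4.2.7.4).

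**Working it through.** The plan states no figure on this point, so there is none to reproduce. The check compares the texts and then uses day arithmetic.

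**1. The two outputs side by side**

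| | Protocol 9.4.4 with Table 4 | SAP 4.2.7.4, Table 14.3.8.2.2 |
|---|---|---|
| Variable | Investigator-judged, clinically significant abnormal | Investigator's category |
| Time points | Each visit | Baseline and last on-treatment ECG |
| Period | Intervention and follow-up | To last dose + 28 days |

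**2. Inputs.** Post-baseline ECGs are scheduled at SV10 (Week 16, Day 113 ± 3) and SV12 (Week 24, Day 169 ± 3), plus E/D (protocol Table 2, SAP 3.5.4). SAP 3.5.2 shows dosing at SV9 (Day 85 ± 3), the last dosing visit. The on-treatment limit is last dose + 28 days (SAP 3.1.4).

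**3. Week 24.** Gap from last dose = SV12 day − SV9 day.

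- Shortest: (169 − 3) − (85 + 3) = 78 days.
- Longest: (169 + 3) − (85 − 3) = 90 days.

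Both exceed 28, so for anyone completing on schedule the Week 24 ECG is always follow-up and never enters the shift table. An earlier last dose only lengthens the gap.

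**4. Week 16.** Let SV9 be on Day 85 + a and SV10 on Day 113 + b, with a and b each from −3 to +3. Gap = (113 + b) − (85 + a) = 28 + b − a.

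- Range: 28 − 6 = 22 to 28 + 6 = 34 days.
- The gap exceeds 28 whenever b > a. Of 7 × 7 = 49 combinations, 7 have b = a, and the other 42 split equally, so 42 / 2 = 21 have b > a.
- 21 / 49 = 43%, if all combinations were equally likely. That is an assumption. Depending on how sites schedule visits, the true share could lie anywhere from 0% to 100%.

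A participant with b > a and no E/D or unscheduled on-treatment ECG has no post-dose ECG in the table. The Week 16 ECG is also lost for a participant who stops dosing early but stays in the study, as protocol 7.1 provides. With a last dose at SV8 (Day 57), for example, Day 113 is 113 − 57 = 56 days later.

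**5. Readings before Week 16.** No ECG is scheduled between Day 1 and Week 16, so only E/D or unscheduled ECGs are at issue. The shift table loses such an abnormality only if a later on-treatment ECG is normal or not clinically significant. A by-visit table alone would not recover it: Table 8 places it in the Week 16 window, and the closest-to-target rule would keep the reading nearer Day 113. The worst-case rule for categorical values in SAP 3.1.4 applies only after that selection.

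**The case against.** The best case on the other side is that the omission is small and other outputs cover most of what matters. Several parts of it stand.

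- **Other by-arm outputs exist.** A reader might infer that ECG abnormalities are never counted by arm or surface only in listings. The documents do not support that. ECG variables are summarised by arm at each visit, and QTcF thresholds are counted by arm over any on-treatment observation (SAP 4.2.7.4). Adverse event tables are by arm and cover on-treatment and follow-up, with adverse events of special interest by arm and maximum grade (SAP 4.2.7.1). A Week 24 arrhythmia reported as an adverse event would be counted. This is not a full substitute: an ECG rated clinically significant is not automatically an adverse event, and the reporting rule in protocol 8.3.6 names laboratory values, spirometry and vital signs but not ECGs.
- **The count can be made by hand.** Appendix 16.2.10.2 lists ECG abnormalities by participant. True, but a listing is not the promised summary.
- **Early transient abnormalities.** A reader might infer that the protocol's by-visit count would catch abnormalities that the shift table hides before Week 16. Under the SAP's windowing rules it would not, as step 5 shows. Among scheduled readings, the protocol and SAP outputs differ at Week 24, and at Week 16 when that visit falls after the 28-day limit.
- **Heart failure.** A reader might infer that monitoring of this named risk is weakened. The plan monitors it by echocardiogram and NT-proBNP (protocol 2.3.1, Table 3), and the study-hold criterion requires echocardiographic confirmation (protocol 4.4.1). The ECG shift table feeds neither.
- **Disclosure elsewhere.** Protocol 9.4 describes itself as a summary and says deviations will be reported in the study report, so SAP Section 6 is not the only place to declare the change. That affects where it is declared, not whether the table is missing.

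**Conclusion.** The point holds, within limits. The protocol's by-visit count of investigator-judged clinically significant abnormal ECGs is absent from the SAP, and SAP Section 6 does not declare the change. The consequence is that the investigator's category at Week 24, one of the two scheduled post-baseline ECG visits apart from E/D, is not tabulated by arm for participants who complete on schedule. The Week 16 category is also lost for those whose ECG falls more than 28 days after the last dose. The Week 24 result follows from the visit windows alone. The size of the Week 16 loss depends on actual scheduling, which the documents do not give; 43% applies only if all in-window day combinations are equally likely.

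The gap is one descriptive safety count. No primary or secondary endpoint and no study-hold criterion depends on it. It is worth correcting because the protocol promised the count, the category is already collected and the correction is cheap.

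**What to change.** In SAP 4.2.7.4 and the Appendix C output list, add a table by treatment group and for total MEDI3506 with:

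- n (%) in each of the three investigator ECG categories at baseline, Week 16 and Week 24, assigned by the analysis visit windows in SAP Table 8 and not by study phase;
- one row for any clinically significant abnormal ECG after first dose through the end of follow-up, including E/D and unscheduled ECGs. This row goes beyond the protocol's by-visit commitment. It is needed because the Table 8 windows and the closest-to-target rule keep only one reading per window.

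The existing shift table can stay. If the sponsor prefers not to add the by-visit table, SAP Section 6 should declare and justify the omission.

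The cost is one or two table shells and no new data. The downside is slightly more tabulation, and the last row will count single transient readings.

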4.2.7.5 Analysis of echocardiogram

Observed values and change from baseline in LVEF will be summarised by visit, by treatment group and for total MEDI3506 using descriptive summary statistics for the As-treated population.

Individual echocardiogram results and abnormalities will be listed.

4.2.7.6 Other safety tests

NT-proBNP results will be summarised with descriptive statistics at each visit and change from baseline summarised for each post-baseline visit for the As-treated population. NT-proBNP results will be also summarised in shift tables comparing maximum value during treatment with baseline value for the As-treated population.

The number of subjects tested positive for SARS-CoV-2 (by PCR or serology test) at end of study, but who were tested negative at baseline visit will also be presented.

Finally, the number of subjects tested positive for SARS-CoV-2 (by PCR or serology test) during the study (including both intervention and follow-up periods) who experienced or not at least one COVID-19 related AEs/SAEs will be provided.

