
5.2 Exclusion Criteria

Participants are excluded from the study if any of the following criteria apply:

Criteria to be Assessed at SV1 and SV2

If any criterion cannot be fully assessed at SV1 and SV2 (eg, laboratory results not yet available), the criterion must be fully assessed prior to randomisation.

Medical Conditions and Diagnostic Assessments

- 1 Participants with a positive diagnostic PCR test for SARS-CoV-2, the virus responsible for COVID-19, at SV2, or anytime on or after Day -7 and prior to SV4.
- 2 Participants with a significant COVID-19 illness within 6 months of enrolment:
 - (a) Participants with a diagnosis of COVID-19 pneumonia based on radiological assessment.

- (b) Participants with diagnosis of COVID-19 with significant findings from pulmonary imaging tests.
 - (c) Participants with a diagnosis of COVID-19 requiring hospitalisation and/or oxygen supplementation therapy.
- 3 Positive hepatitis C antibody, hepatitis B virus surface antigen, or hepatitis B virus core antibody, at screening; or known to have tested positive for human immunodeficiency virus.
 - 4 Evidence of active or untreated latent TB infection (LTBI):
 - (a) Positive interferon gamma release assay (IGRA) test and evidence of symptoms suggestive of active TB.
 - (b) Positive IGRA, or repeated indeterminate IGRAs, no evidence of active TB and untreated for LTBI, unable to be treated for, or declines treatment of LTBI.
 - (c) Participants newly diagnosed with LTBI on initial screening could be considered for rescreening if they complete a full course of treatment for LTBI in accordance with recommended treatment guidelines prior to rescreening. In this situation, repeat IGRA test is not required after completion of treatment for LTBI.
 - (d) Participants with an indeterminate IGRA should undergo a repeat test and if still indeterminate may be enrolled only after being treated for LTBI.
 - 5 This criterion has been removed.
 - 6 An LVEF < 45% measured by echocardiogram during screening.
 - 7 A family history of heart failure defined as either of the following:
 - (a) ≥ 2 first degree relatives with clinically significant heart failure, or
 - (b) ≥ 1 first degree relative with heart failure known to be heritable (eg, hypertrophic cardiomyopathy), unless inheritance is excluded by genetic testing.
 - 8 Major surgery within 8 weeks prior to screening at SV1, or planned inpatient surgery or hospitalisation during the screening, intervention or follow-up periods.

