3.1.7 Derivation of subgroups

Following subgroups will be explored. Any participants with a missing value for the defined subgroup will be excluded from the analysis of that subgroup. Subgroups will only be explored if there is at least 20% of the total participants in that subgroup.

- Gender (male vs female);

- Age by category (≥ 18 to < 50 vs ≥ 50 to < 65);
- Race (as entered in the eCRF);
- BMI (< 19 kg/m², ≥ 19 - < 25 kg/m², ≥ 25 - < 30 kg/m², ≥ 30 kg/m²);
- Geographical region (North America [USA], South America [Argentina], Eastern Europe [Hungary, Poland], Western Europe/Rest of the World [Germany, UK, South Africa]);
- Baseline percent predicted pre-bronchodilator FEV₁ ($< 60\%$ vs $\geq 60\%$);
- Age of asthma onset ($<$ median vs \geq median);
- Number of exacerbations in last 12 months as collected in eCRF (1 vs ≥ 2);
- Smoking status at baseline (never vs former);
- Baseline total ACQ-6 ($<$ median vs \geq median);
- Baseline total SGRQ ($<$ median vs \geq median);
- Baseline ICS total daily dose (< 500 μ g vs ≥ 500 μ g);
- Baseline blood eosinophils ($< 0.3 \times 10^9$ L vs $\geq 0.3 \times 10^9$ L);
- Background medication use (dual therapy vs triple therapy);
- Baseline FeNO (< 25 ppb vs ≥ 25 ppb);
- Baseline Total IgE (≤ 100 kU/L vs > 100 kU/L);
- Baseline mono or poly sensitised to allergen (IgE) (multiple allergens sensitisation vs single allergen sensitisation);
- T2 Corren (high vs low);
- T2 GINA (high vs low);
- SARS-CoV-2 PCR test (positive at any point vs never positive);
- SARS-CoV-2 Serology test (negative at baseline and positive at end of study vs all others);

- CCI [REDACTED]

[REDACTED]

[REDACTED]

[REDACTED]

[REDACTED]

Background medication use

Triple therapy will be defined as the combination of inhaled corticosteroids, long-acting beta-agonist and long-acting anti-muscarinic agent (ICS + LABA + LAMA). Dual therapy will be defined as ICS + LABA.

Allergen sensitisation

For the allergen specific IgE with a qualitative (positive or negative) result, a positive result and total IgE >100 kU/L will define sensitisation. For the allergen specific IgE with a quantitative result, a result equal or greater than 1.41 kU/L and total IgE > 100 kU/L will define sensitisation.

GINA T2 cut-offs

High T2 will be defined as a baseline eosinophil count of $\geq 0.15 \times 10^9$ L and/or elevated baseline FeNO (≥ 20 ppb) and/or at least one allergen sensitisation at baseline.. Other cases will correspond to Low T2.

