3.5.3.1 Other safety tests

- NT-proBNP (only at SV1, SV8, SV9, SV10, SV12 and E/D)
- SARS-CoV-2 PCR test (performed anytime between Day -7 and Day -4 as the results are needed prior to randomisation. Testing may then be performed at any point during the study intervention and follow-up periods for a participant suspected of having COVID-19)

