3.5.3.2 SARS-CoV-2 serology testing

Participants' serum will be tested for the presence of antibodies to the SARS-CoV-2 virus from blood drawn at the visits SV4, SV10 and E/D.

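### SAP 4.2.7.6 and Table 14.3.8.6.1 replace the serology-only SARS-CoV-2 endpoint with a PCR-or-serology count, leave the baseline test unnamed, and do not declare the change

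*SAP*

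**What the plan says.** Protocol Section 3, Table 4, lists this safety endpoint: "Number of participants seropositive for SARS-CoV-2 at end of study who were seronegative at randomisation visit". SAP Section 1.1, Table 1, repeats it. Both the baseline and the end-of-study conditions refer to serology.

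SAP Section 4.2.7.6 plans to present "The number of subjects tested positive for SARS-CoV-2 (by PCR or serology test) at end of study, but who were tested negative at baseline visit". The output list in SAP Appendix C carries the same wording as the title of Table 14.3.8.6.1: "Number of subjects tested positive for SARS-CoV-2 (by PCR or serology test) at end of study who were tested negative at baseline visit". PCR enters the end-of-study condition, and the baseline condition names no test.

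Elsewhere the documents keep the two tests apart:

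- The next endpoint in Protocol Table 4, on COVID-19 adverse events, does pool them: "For participants testing positive for SARS-CoV-2 (by PCR or serology test), during the intervention and follow-up periods". The pooled wording belongs to that endpoint and not to the seroconversion one.
- SAP Section 3.1.7 has a PCR subgroup and, separately, a serology subgroup: "SARS-CoV-2 Serology test (negative at baseline and positive at end of study vs all others".
- SAP Section 3.5.3.2 takes serology from "blood drawn at the visits SV4, SV10 and E/D".
- SAP Section 3.5.3.1 says of PCR after randomisation: "Testing may then be performed at any point during the study intervention and follow-up periods for a participant suspected of having COVID-19".

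SAP Section 6 lists the departures from Protocol Amendment 4.0, including a small edit to the ACQ-6 cut-offs. This change is not among them.

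**The concern.** A named safety endpoint has no planned table that reports it as defined. The table that stands in its place measures something else, and it cannot be programmed without a decision that the SAP does not make: which test must be negative at baseline.

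The two tests also differ in who is tested and when. Serology is scheduled for everyone at fixed visits. By the SAP's account, PCR after randomisation is prompted by suspicion of COVID-19. A pooled count therefore mixes a scheduled measure with a symptom-driven one.

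What is at stake is a safety summary. Protocol Section 2.3.1 names serious infection, including with SARS-CoV-2, as a potential risk of MEDI3506, and Section 8.3.7 lists it among the adverse events of special interest. A reader of the study report would expect this row to show the protocol's quantity.

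**Working it through.** The documents state no expected count or rate for this endpoint, so there is no figure to reproduce. The check compares the definitions and then illustrates how far they could diverge.

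**Definitions side by side**

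| Place | Negative at baseline | Positive at end of study |
|---|---|---|
| Protocol Table 4, SAP Table 1 | serology | serology |
| SAP 3.1.7, serology subgroup | serology | serology |
| SAP 4.2.7.6, Table 14.3.8.6.1 | test not named | PCR or serology |

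**Timing.** Serology has one post-baseline analysis window (SAP Table 9) and is drawn last at SV10 (Week 16) or at early discontinuation. PCR has analysis windows up to Week 24 (SAP Table 3). End of study can therefore mean different dates for the two tests.

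**Baseline PCR.** Protocol Section 5.2 excludes "Participants with a positive diagnostic PCR test for SARS-CoV-2, the virus responsible for COVID-19, at SV2, or anytime on or after Day -7" and before SV4. Eligible participants should therefore all be PCR-negative at entry, so the choice of baseline test matters.

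**Illustration.** N = 228 randomised (Protocol Section 4.1). The following are assumptions, none of them given in the documents: baseline seropositivity s = 10%, 50% or 80%; seroconversion among baseline seronegatives c = 10% or 30%; PCR positivity at end of study q = 0%, 1% or 5%, independent of serology.

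- Protocol definition: N(1−s)c.
- Reading A, both tests negative at baseline: N(1−s)[c + (1−c)q].
- Reading C, the same test goes from negative to positive: reading A plus N·s·q.
- Reading B, a negative PCR at baseline is enough: N{s + (1−s)[c + (1−c)q]}, with baseline seropositives assumed to stay seropositive.

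Worked example with s = 50%, c = 10%, q = 1%:

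- Protocol: 228 × 0.5 × 0.1 = 11.4.
- A: 228 × 0.5 × (0.1 + 0.9 × 0.01) = 12.4.
- C: 12.4 + 228 × 0.5 × 0.01 = 13.6 (from unrounded values).
- B: 228 × [0.5 + 0.5 × 0.109] = 126.4.

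Other points in the grid:

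| s | c | q | Protocol | A | C | B |
|---|---|---|---|---|---|---|
| 10% | 30% | 0% | 61.6 | 61.6 | 61.6 | 84.4 |
| 10% | 10% | 5% | 20.5 | 29.8 | 30.9 | 52.6 |
| 50% | 30% | 5% | 34.2 | 38.2 | 43.9 | 152.2 |
| 80% | 10% | 5% | 4.6 | 6.6 | 15.7 | 189.0 |

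Ratio to the protocol count over the whole grid:

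- A: 1.00 at q = 0%, 1.02 to 1.09 at 1%, 1.12 to 1.45 at 5%. The ratio is 1 + (1−c)q/c and does not depend on s. Its maximum here is 1 + 0.9 × 0.05/0.1 = 1.45.
- C: 1.00 at q = 0%, 1.03 to 1.49 at 1%, 1.14 to 3.45 at 5%.
- B: 1.37 to 41.45. The excess is mostly the N·s participants who were already seropositive at entry.

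**The case against.** The strongest reply is that this is a wording slip with little consequence. Someone seropositive at SV4 did test positive at the baseline visit, so counting that person as newly positive would mean ignoring a result from that day. If baseline-negative is read sensibly as negative on both tests, the only extra participants are PCR positives who did not seroconvert. These are likely few if PCR is done only on suspicion. The protocol count could also be recovered: the serology flag survives in SAP Section 3.1.7, and SAP Section 4.2.7.3 lists all SARS-CoV-2 results. COVID-19 adverse events of special interest have their own tables.

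Much of this stands as a limit on size. It does not remove the mismatch. The SAP does not state the sensible reading, and SAP Table 3 assigns PCR results before the first dose to Baseline, so a programmer could follow either one. The Section 3.1.7 flag serves subgroup analysis of the primary endpoint, subject to a 20% minimum subgroup size, and does not replace a safety table. Being recoverable from a listing is not the same as being reported.

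Two further cautions apply. The PCR schedule is itself unsettled: Protocol Table 2 marks PCR at on-site visits with a footnote about suspected cases, whereas the SAP ties it to suspicion. Nor does serology alone isolate new infection, because Protocol Section 2.3.1.3 generally permits vaccination during the study. That limits interpretation under either definition.

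**Conclusion.** The point holds as a definition mismatch. SAP Section 4.2.7.6 and Table 14.3.8.6.1 report a different quantity from the endpoint in Protocol Table 4 and SAP Table 1, the departure is undeclared, and no planned table carries the defined endpoint.

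Its size cannot be determined from the documents. Under the assumed rates it is 1.00 to 1.45 times the protocol count if both baseline tests must be negative, up to 3.45 times if the same test must change from negative to positive, and 1.37 to 41.45 times if a negative PCR alone suffices.

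A reader might infer three stronger things that the documents do not support:

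- That the two definitions must give very different counts. This needs the reading in which a negative PCR overrides a positive SV4 serology, and the SAP does not state that reading.
- That PCR is pooled on both sides. The SAP's parenthesis attaches to the end-of-study result; the baseline test is simply unnamed.
- That the comparison between arms is biased. This is a descriptive count in a randomised, blinded trial, with no test planned on it and no mechanism for differential error shown.

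The primary analysis, alpha and sample size are unaffected.

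**What to change.** In SAP Section 4.2.7.6 and in the title and shell of Table 14.3.8.6.1, count participants seronegative at SV4 and seropositive at the post-baseline serology sample (SV10 or early discontinuation), using the flag already derived for Section 3.1.7. Show PCR positives after first dose as a separate row if they are wanted.

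If a pooled count is intended, keep it as an additional output. Declare it in SAP Section 6, and state the test and time point for both the baseline and the end-of-study conditions.

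The cost is one sentence of SAP text and one table shell, plus an entry in Section 6 if pooling is kept. No new data are needed.
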